Appendix 5 Percent Bone Marrow Content in Human Skeleton

Percent Bone Marrow in the Adult Skeleton

Woodward Holaday E. A summary of the data of Mechanik on the distribution of human bone marrow. Phys Med Biol. 1960;5:57-59

Appendix 6 Prohibited Traditional Chinese Medicines During the Study Period

Traditional Chinese medicines prohibited during the study include but are not limited to the following:

- ✓ Huatan Huisheng tablet
- ✓ Brucea Javanica oil soft capsule
- ✓ Mandarin melon berry syrup
- ✓ Cantharidin
- ✓ Cinobufotalin
- ✓ Bufotoxin
- ✓ Kang'ai injection
- ✓ Kanglaite injection
- ✓ Zhongjiefeng injection
- ✓ Aidi injection
- ✓ Awei Huapi ointment
- ✓ Kangaiping pill
- ✓ Fukang capsule
- ✓ Xiaoaiping
- ✓ Pingxiao capsule
- ✓ Pingxiao tablet
- ✓ Shendan Sanjie capsule
- ✓ Ankangxin capsule
- ✓ Boshengaining
- ✓ Zedoary turmeric oil and glucose injection
- ✓ Kanglixin capsule
- ✓ Cidan capsule

## ABBREVIATIONS

AE	Adverse event
BOR	Best overall response
CR	Complete response
DCR	Disease control rate
DoR	Duration of response
FAS	Full analysis set
ORR	Objective response rate
PD	Pharmacodynamics
PFS	Progression-free survival
PR	Partial response
SAE	Serious adverse event
SAP	Statistical Analysis Plan
SD	Stable disease
SS	Safety set
TTOR	Time to objective response

## 1 REVISION

None.

## 2 PROTOCOL AMENDMENT

Added overall survival (OS), time to objective response (TTOR), and subgroup analysis as exploratory efficacy analysis to provide guidance for subsequent phase III clinical studies

## 3 INTRODUCTION

This statistical analysis plan is formulated to provide specific statistical analysis and reporting methods or strategies for a phase II study on the efficacy and safety of SHR-1210 plus capecitabine and oxaliplatin sequential treatment (cohort 1) or SHR-1210 plus apatinib (cohort 2) in previously untreated advanced or metastatic gastric or gastroesophageal junction cancer. The final draft of this plan will be completed before database locking and will be signed by various functional departments for confirmation.

### 3.1 Study Design

This is a randomized, open-label, multi-center, phase II clinical study.

A total of 98 patients with previously untreated advanced or metastatic gastric cancer or gastroesophageal junction cancer will be enrolled. Subjects will be randomized to receive sequential therapy of SHR-1210 plus capecitabine and oxaliplatin (cohort 1, n = 43) or SHR-1210 plus apatinib treatment (cohort 2, n = 55).

Cohort 1 (sequential therapy of SHR-1210 combined with capecitabine and oxaliplatin): SHR-1210 + capecitabine + oxaliplatin for 4-6 cycles, followed by SHR-1210 + apatinib for subjects without progressive disease (PD);

Cohort 2 (SHR-1210 combined with apatinib): SHR-1210 + apatinib.

A two-stage design is adopted to minimize the exposure of subject to ineffective treatment. Nineteen subjects will be enrolled into cohort 1 and cohort 2 at the first stage, respectively. If at least 4 subjects achieve objective response (complete response or partial response), the second stage will be initiated. And more subjects will be enrolled in cohort 1(to 43 subjects) and in cohort 2 (to 55 subjects), respectively.

In this study, the screening period should be no more than 28 days. After completing screening examinations and assessments, eligible subjects will enter the treatment period (21 days/cycle) and begin the study treatment and study visits according to the protocol. Tumor imaging assessment will be performed once in every 2 cycles (6 weeks  $\pm$ 7 days) during the first 12 months (the first 16 cycles) of the study treatment period and once every 3 cycles (9 weeks  $\pm$  7 days) thereafter. The subjects will complete safety examinations and imaging assessments upon discontinuation of the study treatment.

Thereafter, the subjects will enter the follow-up period. The safety follow-up period will start after the last administration, and the subjects are followed up every 30 days ( $\pm 7$  days) until 90 days after the last administration. The first safety follow-up will be carried out at the study site; the second and the third follow-up visits will be made via telephone calls. The survival follow-up period starts after the end of the safety follow-up period. The survival follow-up period ends upon the subject's death, lost to follow-up, withdrawal of informed consent, or study termination by sponsor. During this period, a follow-up will be conducted every month via telephone or other effective methods to collect information on subject survival and subsequent treatments. For subjects who show no evidence of radiographic progression, an imaging evaluation should continue at the frequency of response evaluations specified in the protocol, until progressive disease, death, lost to follow-up, withdrawal of informed consent, start of other anti-cancer treatments, or trial termination by the sponsor.

All subjects should continue to receive the study treatment until progressive disease, intolerable toxicity, voluntary treatment discontinuation or study withdrawal by the subject, or discontinuation determined by the investigator.

SHR-1210 is an immune checkpoint inhibitor and according to the experience of drugs of same class, some subjects may experience delayed or early pseudoprogression after receiving immunotherapy drugs. Therefore, if subjects in the treatment group who have experienced progressive disease (PD) for the first time meet the criteria for continuing treatment after progressive disease, they can continue to be treated according to the original treatment regimen. Subjects who do not have progressive disease or intolerable toxicities may continue the SHR-1210 treatment for no more than 24 cumulative months.

Subjects who do not have progressive disease after 24-month treatment may continue the apatinib monotherapy according to the prescribing information of apatinib.

### **3.2 Study Objectives**

#### **3.2.1 Primary objective**

To evaluate the efficacy of the sequential therapy of SHR-1210 combined with capecitabine and oxaliplatin or SHR-1210 combined with apatinib mesylate as the first-line therapy for advanced or metastatic gastric (GC) or gastroesophageal junction (GEJ) cancer.

#### **3.2.2 Secondary objective**

To evaluate the safety of the sequential therapy of SHR-1210 combined with capecitabine and oxaliplatin or SHR-1210 combined with apatinib mesylate for the treatment of advanced or metastatic gastric (GC) or gastroesophageal junction (GEJ) cancer.

## 4 INTERIM ANALYSIS, FINAL ANALYSIS, AND UNBLINDING

### 4.1 Interim Analysis

At the end of Stage I of this study, it will be judged whether to continue the trial in a certain cohort according to the rules in Section 5.

### 4.2 Final Analysis

The final analysis will be performed after the database is locked and released.

### 4.3 Unblinding

This is an open-label clinical study and does not involve unblinding.

## 5 STATISTICAL HYPOTHESES AND DECISION RULES

Cohort	H0	H1	N1	R1	N	R	Power	Alpha
Cohort 1	35% ORR	55% ORR	19	4	43	21	80%	0.05
Cohort 2	15% ORR	30% ORR	19	4	55	13	80%	0.05

N1: Number of subjects at the first stage;

R1: The minimum effective number of subjects required in Stage I; if the effective number of subjects in Stage I is less than R1, the trial will be discontinued because of invalidity. If  $\geq 4$  subjects in cohort 1 show disease response (CR or PR), the study will enter Stage II and 24 subjects will be added. If  $\geq 4$  subjects in cohort 2 show disease response, the study will enter Stage II and 36 subjects will be added (55 subjects in cohort 2).

N: Final number of subjects;

R: The minimum effective number of subjects eventually required. If the total effective number of subjects is less than R after the end of Stage II (cohort 1 fails to show at least 21 subjects of disease responses, and cohort 2 fails to show at least 13 subjects of disease responses), subsequent drug study will be not considered necessary.

## 6 ANALYSIS SETS

### 6.1 Full Analysis Set (FAS)

It includes all subjects who are randomized and have received study drugs at least once. This analysis set will be used for the efficacy analysis.

### 6.2 Per-Protocol Set (PPS)

It is a subset of the full analysis set, and subjects with important protocol deviations judged to have a significant impact on treatment efficacy will be excluded from this set. The list of subjects included into or excluded from the PPS should be reviewed and determined by the sponsor and the investigator before the database is locked.

### **6.3 Safety Analysis Set**

It includes all enrolled subjects who have received the study drugs at least once and have post-administration safety evaluation data.

### **6.4 Evaluable Set**

It is a subset of FAS and includes all enrolled subjects who have received the study drugs at least once and have at least one post-baseline tumor assessment.

### **6.5 PK Analysis Set (PKS)**

It includes all enrolled subjects who have received the study drugs and have post-administration PK evaluation data (concentration and/or parameter).

### **6.6 Immunogenicity Analysis Set (ADA)**

It includes all enrolled subjects who have received the study drugs at least once and have baseline and at least one set of post-baseline ADA evaluation data.

## **7 MISALLOCATION OF TREATMENT GROUPS**

Not applicable.

## **8 PROTOCOL DEVIATION**

The protocol deviation analysis is based on FAS. Protocol deviations may include but are not limited to the following types:

- Not meeting the inclusion/exclusion criteria;
- Meeting the withdrawal criteria but the subject has not withdrawn from the study;
- Not taking study drugs according to the protocol, such as taking wrong doses and missed doses;
- Using combined medications prohibited by the protocol, such as other anti-tumor drugs and adjuvant drugs related to tumor treatment (including anti-cancer Chinese medicine);
- Non-compliance to the procedures stipulated in the protocol, such as omission of blood sample collection, and blood sample collection time exceeding the time window.

In addition, the list of subjects experiencing protocol deviations should be reviewed and confirmed before the database is locked.

The corresponding listing of subjects excluded from PPS due to important protocol deviations will be reported.

## 9 EVALUATION ENDPOINTS

### 9.1 Efficacy Endpoints

#### Primary endpoint:

- **Objective response rate (ORR):** the percentage of participants in the analysis population who have a complete response (CR) or a partial response (PR).

#### Secondary endpoints:

- **Progression free survival (PFS):** the time from the start of study treatment (the time of the first administration provided by the investigator) to the time of objective progressive disease or death due to any cause, whichever occurs first.
- **Duration of response (DoR):** the time from first evidence of CR or PR until first evidence of disease progression or death due to any cause. The date of response is the date of first documented response rather than the date of confirmation.
- **Disease control rate (DCR):** the percentage of participants in the analysis population who have CR, PR, or stable disease (SD).

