4.3 Randomization and Blinding

Only Patients who meet all the inclusion criteria shall be randomly enrolled in this study. In the event that an ineligible patient is randomized, or erroneously start the treatment, or an enrolled subject no longer meets the eligibility criteria before starting the study treatment, the sponsor's representative and the investigator must jointly discuss whether the subject should continue or withdraw from the study. The sponsor should ensure that appropriate documentation is retained with regards to such decisions.

This study is an open-label study and does not involve blinding.

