Progression-free survival (PFS): The time between the date of enrollment and the first documented tumor progression (as per RECIST 1.1 criteria, regardless of whether treatment is continued), or death due to any cause, whichever occurs first. When determining PFS, clinical exacerbations without definite evidence of progressive disease (as per RECIST 1.1) is not considered progressive disease. For subjects who die without any prior reports of progression, the date of death is considered the date of progression. Subjects without progressive disease or death will be censored on the date of their last evaluable tumor assessment. Subjects without tumor assessments during the study or death will be censored on their date of enrollment. Subjects who discontinue the treatment for reasons other than progressive disease (no subsequent tumor assessments) will be censored on their date of study discontinuation. For subjects who have not previously reported progressive disease but have initiated subsequent anti-tumor therapy, they will be censored on the date of their last evaluable tumor evaluation before starting the subsequent anti-tumor therapy, or they will be censored when starting the subsequent anti-tumor therapy. When subjects are not censored on the date of study discontinuation or the date of starting new anti-tumor treatment, the

scheduled sensitivity analysis will confirm PFS based only on the time of radiologically confirmed progression events. The occurrence of a new tumor will not be considered a progressive disease and is not censored.

Disease control rate (DCR): the proportion of subjects with a best overall response of complete response (CR), partial response (PR), or stable disease (SD) as per RECIST 1.1 criteria. If the subject achieves CR or PR, confirmation should be done at least 4 weeks (28 days) after the first evaluation. Best overall response refers to the best response assessed by the investigator, or the best response from the date of enrollment to the first documentation of progression as per RECIST 1.1 or to the start of a new anti-tumor treatment (whichever comes first). For subjects without documented progression or new anti-cancer treatment, BOR will be determined based on all response evaluations. For subjects who continue SHR-1210 treatment beyond progression, the best overall response should be based on the efficacy assessment at the time of first documented progression as per RECIST 1.1.

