8.1 Statistical Analysis Plan

The primary objective of this study is to evaluate the efficacy of the sequential therapy of SHR-1210 combined with capecitabine and oxaliplatin (cohort 1) or SHR-1210 combined with apatinib mesylate (cohort 2) as a first-line treatment for advanced or metastatic Gastric (GC) or gastroesophageal junction (GEJ) cancer. The primary efficacy endpoint is ORR.

Detailed summaries and methods of statistical analyses for the data collected from the study shall be included in the statistical analysis plan (SAP), which shall be finalized and filed by the sponsor. The SAP should be revised accordingly if there are any changes to the study protocol that may have a major impact on the SAP, as determined by the sponsor or principal investigator. Relevant content in statistical analysis plan that is relevant to this protocol may be revised. However, if revised content involves the main and/or key factors of the protocol (such as the definition of endpoints or their analysis), such content in the protocol will be revised.

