### 11.5.2.3 Progression free survival (PFS)

PFS refers to the time from the start of randomization to the date of objective progressive disease or death (caused by any reason), whichever occurs first. [Table 3](#) describes progressive disease, death, or censoring.

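### The SAP gives PFS two time origins, and the protocol and SAP censor it differently, so this secondary endpoint is not uniquely defined

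*SAP*

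**What the plan says.** **Time origin**

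- SAP 9.1, secondary endpoints: PFS is "the time from the start of study treatment (the time of the first administration provided by the investigator") to progression or death.
- SAP 11.5.2.3: "PFS refers to the time from the start of randomization to the date of objective progressive disease or death". The first row of Table 3 also censors at randomisation, and SAP 11.5.3 runs OS and time to response from randomisation.
- Protocol 7.1.1: "The time between the date of enrollment and the first documented tumor progression". Enrolment is not defined as a date. Protocol 4.3 says "Only Patients who meet all the inclusion criteria shall be randomly enrolled in this study".

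**Censoring**

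- Protocol 7.1.1 censors at the last evaluable scan by default. Subjects who stop treatment for a reason other than progression, and have no later tumor assessment, "will be censored on their date of study discontinuation". For new therapy it gives the last evaluable scan beforehand, "or they will be censored when starting the subsequent anti-tumor therapy". The DoR definition in the same section repeats that choice. On deaths it says: "For subjects who die without any prior reports of progression, the date of death is considered the date of progression". It has no rule for long gaps.
- SAP Table 3 censors at the last objective assessment in the first two situations. It also censors progression or death recorded after more than two missed evaluations, which it equates to 98 days.

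**Which text governs**

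Protocol 8.1 says the protocol itself will be revised "if revised content involves the main and/or key factors of the protocol (such as the definition of endpoints or their analysis"). SAP section 2 declares only OS, time to response and subgroups as changes. Neither document says which PFS definition prevails.

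**The concern.** The same subject can receive a different PFS time, or a different event status, depending on which section the programmer follows. The full analysis set requires both randomisation and a dose (Protocol 8.3, SAP 6.1). Both origins can therefore be computed for every analysed subject, and no missing date would expose the conflict. If SAP 9.1 were followed, PFS and OS would run on different clocks in the same subjects.

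DoR is drawn in as well, because SAP 11.5.2.2 requires the end of response to agree with the PFS date. At stake are the reproducibility of the PFS and DoR results and the comparison of the median PFS with other studies.

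**Working it through.** The documents give no sample size, event count or power for PFS, so there is no planned figure to reproduce. The check compares the rules and does day arithmetic. Months are days/30.4375, the divisor in SAP 11.5.3.1.

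**1. Time origin.** Starting at first dose shortens each PFS time by the interval from randomisation to first dose. No such interval is stated, so I assume 1 to 7 days.

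- 1/30.4375 = 0.03 months; 7/30.4375 = 0.23 months.
- Against the 6.6-month median that Protocol 1.2 cites for a first-line chemo-immunotherapy cohort: 0.03/6.6 = 0.5% and 0.23/6.6 = 3.5%.
- Outer bound: screening runs to the start of treatment and lasts at most 28 days, so 28/30.4375 = 0.92 months.

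**2. Censoring rules side by side**

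| Situation | Protocol 7.1.1 | SAP Table 3 |
|---|---|---|
| (a) Stops without PD, no later scan | Study discontinuation date | Last objective assessment |
| (b) PD or death after a gap over 98 days | Event | Censored at last scan before the gap |
| (c) New anti-tumor therapy | Last scan before it, or its start date | Last scan before it |
| (d) No post-baseline scan, alive | Enrolment date | Randomisation only if baseline is missing; otherwise the baseline scan |

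In (d) the baseline scan may precede randomisation, which gives zero or negative time.

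**3. Size of (a).** Example: last scan day 84, stops without PD on day 100, no later scan. The protocol censors at day 100 and Table 3 at day 84, a difference of 16 days (0.53 months). Protocol 6.2 and 6.3 require a withdrawal scan unless one was done within 4 weeks. With that scan done, the difference is about 28 days or less (28/30.4375 = 0.92 months). If scans are missed it can be longer.

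The effect on the Kaplan-Meier curve can be smaller still. I assumed:

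- exponential progression with a median of 4 or 6.6 months;
- exponential discontinuation with a median of 12 or 24 months;
- scans exactly on schedule, and no deaths between scans.

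Between 16.1% and 37.9% of subjects were then censored for stopping. PFS at day 183 was identical under both rules in all four settings (0.3864, 0.3825, 0.5519, 0.5627). This is expected: moving a censoring date between two consecutive scans changes no risk set at an event time. Off-schedule scans and deaths between scans would break the equality.

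**4. Size of (b).** Example: last scan day 84, scans at days 126 and 168 missed, PD at day 210. The gap is 210 − 84 = 126 days, which exceeds 98. The protocol records an event at day 210 (6.90 months). Table 3's day limit censors at day 84 (2.76 months). Only two scans were missed, so Table 3's own wording of more than two would keep the event.

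**5. Does 98 days match the wording?** Scans are every 42 ± 7 days for 16 cycles (16 × 21 = 336 days), then every 63 ± 7 days.

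- 6-week schedule: the longest in-window gap with one missed scan is 2 × 42 + 14 = 98 days. A gap over 98 days therefore means two or more missed, not more than two.
- 9-week schedule: one missed scan gives a nominal gap of 2 × 63 = 126 days (112 to 140 within windows). A single missed scan already exceeds 98. For example, with the last scan at day 399, day 462 missed and PD at day 525, the gap is 126 days and the event is lost.

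The limit matches the wording on neither schedule.

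**6. Sensitivity analysis.** Protocol 7.1.1 schedules a PFS sensitivity analysis based on radiologically confirmed progression. The SAP contains none.

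**The case against.** The strongest reply is that PFS is secondary and descriptive. It is summarised by Kaplan-Meier within cohort, with no test, no comparison and no PFS-based sample size. Go/no-go and success depend on ORR alone (Protocol 8.2, SAP 5). That stands, and it limits the weight of the point.

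A reader might infer more than the documents support in four ways:

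- **Three settled origins.** Protocol 4.3 treats enrolment and randomisation as one step, so there are probably two distinct origins, with SAP 9.1 the outlier. The missing definition is still a gap.
- **A free choice of definition after seeing open-label data.** The operative analysis section, its table and the OS definition all use randomisation, and the SAP must be final before database lock. The contradiction is nevertheless inside the SAP, so finalising it as written would not remove it.
- **A full scan interval of unobserved time (42 to 63 days, 1.4 to 2.1 months) for everyone who stops without progression.** The protocol's rule covers only those with no later assessment. Scans are meant to continue after stopping, and a withdrawal scan is required. One interval is not a valid bound if scans are missed either.
- **A contradiction over new therapy.** The SAP selects one of two dates that the protocol permits. What remains is an unresolved alternative in the protocol, for both PFS and DoR.

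First dose is also a defensible origin, since every analysed subject is dosed and the cohorts are not compared. Consistency is what is required. Randomisation needs the fewest edits.

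**Conclusion.** The inconsistency is real and should be corrected, but it is moderate in weight. The SAP contradicts itself on the PFS origin, and the protocol and Table 3 give different results for subjects who stop without a later scan and for events after a long gap. Protocol 8.1 calls for an endpoint change to be carried into the protocol, and this was not done.

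The origin conflict alone is minor, on the assumed 1 to 7 day interval. The 6.6-month median used for scale comes from 25 subjects on another PD-1 antibody with cisplatin-based chemotherapy, and does not represent cohort 2. Item (a) is small per subject when scans are done as required. Item (b) carries most of the weight, because it turns events into censored observations and its day limit disagrees with its own wording. How many subjects it would affect cannot be derived from the documents.

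**What to change.** Before database lock:

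1. Change SAP 9.1 to randomisation, matching SAP 11.5.2.3, Table 3 and OS. State in Protocol 7.1.1 that enrolment means the randomisation date.
2. In Protocol 7.1.1, censor subjects without an event, and those starting new therapy, at the last evaluable tumor assessment. Delete the discontinuation-date rule and the new-therapy alternative, the latter for DoR as well.
3. In both documents, censor at randomisation when there is no post-baseline scan and no death.
4. Reconcile the gap rule, since adopting Table 3 unchanged would import its flaw. Express it as two or more consecutive missed scheduled assessments. Day limits that fit the windows are 2 × 42 + 14 = 98 days on the 6-week schedule and 2 × 63 + 14 = 140 days on the 9-week schedule. A gap spanning the switch needs 42 + 63 + 14 = 119 days. Apply the same rule in SAP Table 2 for DoR.
5. Carry the protocol's PFS sensitivity analysis into the SAP.

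The cost is protocol and SAP wording plus the matching PFS and DoR derivations. No new data, visits or subjects are needed, and the ORR design is untouched.
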